6.3 Dose Escalation Guidelines

6.3.1 Dose-limiting Toxicities Observation Period

The DLT observation period for the Phase 1 cohorts will be the first cycle during IMCgp100 dosing (C1D1 until C1D28).

6.3.2 Starting Dose Rationale

6.3.3 Dose Levels

This study will begin with Phase 1 dose escalation of the intra-patient escalation dosing regimen to assess the safety and tolerability of the C1D15 intra-patient escalation. [REDACTED]

6.3.4 Dose Escalation Guidelines

Three to 6 patients will be enrolled in sequentially enrolling dose cohorts (see Table 6-2 dose levels). In each cohort, patients will be treated during Cycle 1 with IMCgp100 as a single agent (Days 1 and 8 of Cycle 1, all patients receive the 20 and 30 mcg, retrospectively). At C1D15, the intra-patient dose escalation will begin. The study will begin with Cohort 1 (See Table 6-2 dose levels) receiving dose level 1 (54 mcg) at CD15 and thereafter. Other cohorts enrolling after Cohort 1 will follow the dose escalation guidelines. Cohorts will enroll to escalation by increments of 10 mcg until an MTD and/or RP2D-IE for the intra-patient dose escalation regimen is identified.

An individual cohort will initially enroll 3 to 6 patients. If none of the 3 patients experiences a DLT, then dose escalation decision may proceed after agreement among study team members (participating investigators and Sponsor) within the DETC. The decision to escalate the dose will be determined based on available toxicity, PK, and pharmacodynamic data following a discussion among members of the study team (all participating investigators and Sponsor Medical Monitor) during DETC. The cohort will be expanded to 6 patients if DLT is observed during the DLT period according to the dose escalation rules noted below. If toxicity is managed adequately to resume IMCgp100 dosing, patients experiencing DLT may continue treatment with IMCgp100 only after agreement with the Sponsor Medical Monitor. Patients in the Phase 1 cohorts will be considered evaluable for dose escalation decisions (DLT Analysis Set) if they receive a minimum of 3 doses of IMCgp100 (with 2 of the 3 doses at the escalated level of C1D15 and thereafter) or have experienced DLT during the DLT observation period.

Dose-escalation in the study will occur after the study team (Sponsor and investigators) have jointly reviewed available safety data for the 3 to 6 patients at the current dose level at a safety team DETC. The decision to dose-escalate will be taken by the study team (participating investigators and the Sponsor Medical Monitor). Additional cohorts may be added if necessary to explore alternate/intermediate dose levels if deemed necessary by the members of the dose escalation teleconference.

6.3.4.1 Dose Escalation Decision Making

Dose-escalation decisions will be made based on treatment-emergent AE, clinical laboratory data, and available PK, and pharmacodynamic data after all patients in a cohort complete the 28-days of study treatment in Cycle 1. Safety data from patients on preceding cohorts will also be taken into consideration. The data will be reviewed and a decision taken whether or not to proceed to the next dose cohort (at the planned or an alternative dose level), whether more patients are required to be dosed at the dose level under review or whether the MTD and/or the optimal RP2D-IE has been reached.

The following dose-escalation rules will be used:

If none of the first 3 evaluable patients experiences a DLT by the end of the DLT observation period, the dose will be escalated and the next cohort of patients can start treatment at the next highest dose level.

- If 1 of the first 3 patients experiences a DLT in Cycle 1, the cohort will be expanded to 6 patients. If none of these additional patients experiences a DLT, then the dose will be escalated to the next higher dose level
- If 2 or more patients in the dose level experience a DLT in the DLT observation period, then the MTD has been exceeded and 3 more patients will be treated at the next lower dose level, if only 3 patients were previously treated at that dose level
- If 0 or 1 DLT is observed at this lower dose level, this dose will be determined to be the MTD
- If 2 DLTs occur at this level, the next lower dose will need to be evaluated similarly
- A minimum of 6 patients will be evaluated at the dose level identified as the RP2D-IE in this study

6.3.4.2 Definition of MTD and RP2D-IE

The **MTD** is defined as the highest dose level with an observed incidence of DLT in fewer than 33% of the patients enrolled in a cohort level. If all evaluated dose levels demonstrate an observed incidence of DLT in fewer than 33% of patients, the MTD has not been reached. If this proves to be the case, then a total of 6 patients will be treated at the highest dose tested to gain additional safety data before proceeding to the dose-expansion part of the study. If a DLT occurs at the MTD, a total of 6 patients must be treated at the MTD.

Determination of the **RP2D-IE** will be based on the sum of the safety, tolerability, pharmacodynamic and PK data, as well as preliminary efficacy data emerging over the course of the Phase 1 testing. The MTD and RP2D-IE may be not be the same dose level for implementation in the UM expansion cohort.

The **RP2D-IE** will be based on the sum of the safety, tolerability, pharmacodynamic, and PK data, as well as preliminary efficacy data emerging over the course of the Phase 1 testing. The RP2D-IE will be defined as the dose level selected for testing in the expansion cohort by the study team, based on all available safety, tolerability, PK, and pharmacodynamic data. The MTD and RP2D-IE may not be the same dose level; the RP2D-IE will be the same dose or a lower dose than an identified MTD. If the MTD and RP2D are different, the RP2D-IE will be implemented in the expansion cohorts. A minimum of 6 patients will be

treated at the identified RP2D-IE for the DLT period before the expansion cohorts with this dose can begin enrollment.

During the course of the UM expansion cohorts, if the rate of grade 3 and/or grade 4 toxicity is considered related to the study drugs and meeting the definition of DLT is higher than 30%, a safety teleconference will be convened with the study team (Sponsor and investigators) to determine if the cohort should continue enrollment.

6.3.4.3 Replacement of Patients

Patients will be replaced in the Phase 1 cohorts according to the guidelines for Phase 1 dose escalation. Patients deemed not eligible for the DLT Analysis Set in Phase 1 will be replaced.

6.4 Definition of Dose-limiting Toxicities

A DLT is defined as an AE or abnormal laboratory value assessed as having a suspected relationship to study drug, and unrelated to disease, disease progression, inter-current illness, or concomitant medications that occurs within the first cycle of treatment, and meets any of the criteria included in [Table 6-3](#). NCI CTCAE version 4.03 will be used for all grading unless otherwise specified. The investigator must notify the Sponsor immediately of any unexpected NCI CTCAE grade ≥ 3 AEs or laboratory abnormalities. Prior to enrolling patients into a higher dose level, all NCI CTCAE grade ≥ 2 AEs will be reviewed for all patients at the current dose level by the study team at the DETC.

Table 6-3 Criteria for Defining Dose Limiting Toxicities

DLTs include any related AE of NCI CTCAE grade 3 or higher occurring in the first cycle of weekly IMCgp100, during the dose escalation Phase 1 part of the study with the following exceptions:	
Hematology	Neutropenia is a DLT if it is NCI CTCAE grade 4 Thrombocytopenia is a DLT if it is NCI CTCAE grade 4 Anemia is a DLT if it is NCI CTCAE grade 4 Lymphopenia of grade ≥ 3 persistent for more than 14 days or the presence of an infection indicating clinically significant lymphopenia Febrile neutropenia of grade ≥ 3 is a DLT
Hepatic	NCI CTCAE grade ≥ 2 total bilirubin with NCI CTCAE grade ≥ 2 ALT is a DLT NCI CTCAE grade 3 elevation of ALT and/or AST is a DLT if a concurrent elevation of bilirubin is observed (\geq grade 1) or if the elevated ALT and/or AST is not resolved to grade ≤ 1 within 72 hours Grade 4 elevation of ALT and/or AST is a DLT
Gastrointestinal	Nausea and vomiting are DLTs if they are NCI CTCAE grade ≥ 3 for > 2 days despite optimal anti-emetic therapy Diarrhea is a DLT if it is NCI CTCAE grade ≥ 3 for > 2 days despite optimal anti-diarrhea treatment
Hypotension	NCI CTCAE grade 3 hypotension is a DLT if not resolved to \leq grade 1 within 24 hours of the dose administration. Any event of hypotension requiring pharmacologic blood pressure support of any duration is a DLT. NCI CTCAE grade 4 hypotension of any duration is a DLT
Hypertension	NCI CTCAE grade 3 hypertension is a DLT if it persists > 7 days despite treatment. Grade 4 hypertension of any duration is a DLT
Infection	NCI CTCAE grade 3 infection or fever in the absence of neutropenia are DLTs if they persist > 5 days. Grade 4 infection of any duration is a DLT
Tumor flare	Grade 3 inflammatory reaction at a tumor site associated with a local anti-tumor immune response is a DLT if not resolved to grade ≤ 2 within 7 days
Electrolytes	NCI CTCAE grade 3 electrolyte abnormalities are DLTs if they persist > 7 days despite treatment or are clinically significant. Grade 4 electrolyte abnormality of any duration is a DLT
Rash and/or photosensitivity	NCI CTCAE grade 3 rash is a DLT if rash persists > 7 days despite optimal treatment. Grade 4 cutaneous toxicity of any duration is a DLT
Fatigue	Fatigue is a DLT if it is NCI CTCAE grade ≥ 3 and lasts > 7 days
Infusion-related reaction	Grade 3 infusion-related reaction will not be considered a DLT if resolved with appropriate medical management within 6 hours of occurrence. Grade 4 infusion reaction is a DLT
Other AEs	Other clinically significant toxicities, including a single event or multiple occurrences of the same event that lead to a dosing delay of > 7 days in Cycle 1, may be considered to be DLTs by the investigators and Sponsor, even if not

	NCI CTCAE grade 3 or higher. Infusion reactions will not be considered as dose limiting because they are idiosyncratic and not related to dose
--	------------------------------------------------------------------------------------------------------------------------------------------------

AE = adverse event; ALT = alanine aminotransferase; DLT = dose limiting toxicity; NCI CTCAE = National Cancer Institute Common Terminology Criteria for Adverse Events.

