If 2 or more patients experience moderate-to-severe acute infusion reactions on C1D1 or if > 25% of patients experience mild infusion reactions, then mandatory primary prophylaxis regimens (i.e., before dosing on C1D1 or C1D15) will be instituted for subsequent patients beginning treatment after discussion and agreement among principal investigators and the Sponsor. Primary and secondary prophylaxis regimens will include both paracetamol/acetaminophen and an antihistamine. The decision taken to mandate primary prophylaxis will be communicated in writing to all principal investigators participating in the study.

Acute allergic reactions should be treated as needed using institutional guidelines. In the event of anaphylactic/anaphylactoid reactions, any therapy necessary to restore normal cardiopulmonary status should be implemented immediately. Such acute allergic reactions will be reported to the Sponsor in an expedited manner. These should be designated as reportable as a SAE regardless of hospitalization as medically important events. Please refer to SAE reporting section for details. The individual symptoms of

the infusion-related reaction should be captured in order to best characterize the study drug infusion reactions, unless the investigator considers another category, such as “allergic reaction,” “anaphylaxis,” or “cytokine release syndrome” more appropriate in a specific situation.

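### Table 6-3 makes Grade 4 and unresolved Grade 3 infusion reactions DLTs, but the last sentence of its Other AEs row, read literally, excludes infusion reactions of every grade

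*Protocol*

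**What the plan says.** Section 6.4 of the protocol defines a DLT as a related first-cycle event that satisfies at least one of the criteria in Table 6-3. The table header sets the general rule, "DLTs include any related AE of NCI CTCAE grade 3 or higher occurring in the first cycle of weekly IMCgp100", and the rows list exceptions and refinements by type of toxicity.

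Two rows deal with infusion reactions:

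- The infusion-related reaction row exempts one case: "Grade 3 infusion-related reaction will not be considered a DLT if resolved with appropriate medical management within 6 hours of occurrence". It then adds, without condition, "Grade 4 infusion reaction is a DLT".
- The Other AEs row lets the investigators and Sponsor classify further clinically significant toxicities as DLTs at their discretion. This includes events below Grade 3, and events that delay dosing by more than 7 days in Cycle 1. The row ends: "Infusion reactions will not be considered as dose limiting because they are idiosyncratic and not related to dose".

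The definition is used in three places. Sections 4.4 and 9.5.1 make DLT incidence the Phase 1 primary endpoint. The stopping rule in Section 6.3.4.1 begins "If 2 or more patients in the dose level experience a DLT in the DLT observation period" and concludes that the MTD has been exceeded. Section 6.3.4.2 carries the definition into Phase 2: if the rate of related Grade 3 or 4 toxicity "meeting the definition of DLT is higher than 30%, a safety teleconference will be convened with the study team".

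**The concern.** The closing sentence of the Other AEs row carries no grade, no duration and no reference to the row above it. Its stated reason, that these reactions are idiosyncratic and unrelated to dose, applies equally at Grade 1 and Grade 4. Taken at its word, it removes from the DLT count the same Grade 4 reaction that the preceding row puts in. It also removes a Grade 3 reaction lasting beyond 6 hours, which the header counts because no exception covers it.

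At stake is whether the Phase 1 primary endpoint, and the Phase 2 safety trigger that borrows its definition, can be applied the same way by two people reading the same table. The trigger concerns related Grade 3 and 4 toxicity only, which is where the two rows disagree.

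**Working it through.** The plan states no figure that depends on this point, so there is none to reproduce. The check is a comparison of the rules, followed by arithmetic on what one reclassified patient could do.

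**Step 1. Classify each kind of related infusion reaction in Cycle 1 under both readings.**

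| Reaction | Header plus infusion-related reaction row | Last sentence of Other AEs row, read literally |
|---|---|---|
| Grade 1–2 | Not a DLT by grade | Not a DLT |
| Grade 3, resolved within 6 hours | Not a DLT (exempted) | Not a DLT |
| Grade 3, not resolved within 6 hours | DLT (header, no exception applies) | Not a DLT |
| Grade 4 | DLT (stated in the row) | Not a DLT |

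The readings agree on the first two lines and disagree on the last two. Different terms do not explain the disagreement, because the infusion-related reaction row itself uses both infusion-related reaction and infusion reaction.

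**Step 2. Phase 1: effect of one reclassified patient.** The rules in Section 6.3.4.1 count patients, and cohorts have 3 to 6 patients.

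- Patient with no other DLT, n = 6: 1/6 = 16.7 percentage points.
- Patient with no other DLT, n = 3: 1/3 = 33.3 points.
- Patient who also has another DLT: 0 points.

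The sensitive case is a six-patient cohort in which one other patient has a DLT. The incidence goes from 1/6 = 16.7% to 2/6 = 33.3%. That meets the rule of two or more patients, and it is no longer below the 33% that Section 6.3.4.2 requires of the MTD.

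**Step 3. Phase 2: the trigger of more than 30%.** Section 6.3.4.2 gives no denominator. Assuming the planned sizes in Section 3.1 (about 20 in Cohort A, 130 in Cohort B, 150 in total):

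- Cohort A: 0.30 × 20 = 6, so at least 7 patients (35.0%). One patient is 1/20 = 5.0 points.
- Cohort B: 0.30 × 130 = 39, so at least 40 patients (30.8%). One patient is 1/130 = 0.8 points.
- Both: 0.30 × 150 = 45, so at least 46 patients (30.7%). One patient is 1/150 = 0.7 points.

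**Step 4. What limits these figures.** Sections 3.1 and 3.2 record that Phase 1 enrollment is complete and that 68 mcg was chosen. The protocol reports no Grade 4 or unresolved Grade 3 infusion reaction whose classification was in doubt, so the realised Phase 1 effect may be zero. Section 6.2 also says that the individual symptoms of "the infusion-related reaction should be captured in order to best characterize the study drug infusion reactions", unless the investigator prefers a category such as cytokine release syndrome. A reaction recorded by its symptoms falls under other rows with their own criteria, for example "Any event of hypotension requiring pharmacologic blood pressure support of any duration is a DLT". How many reactions are recorded that way is not stated.

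**The case against.** The strongest reply is that the protocol, read as a whole, already shows which row governs.

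- Under Section 6.4 an event need satisfy only one of the table's criteria. A Grade 4 infusion reaction satisfies the row written for it, and an unresolved Grade 3 reaction satisfies the header.
- The disputed sentence stands in the residual row, directly after the clause on discretionary DLTs below Grade 3. It is natural to read it as keeping lower-grade infusion reactions out of that discretionary route. The unlimited reading would deprive the infusion-related reaction row of any effect.
- Table 6-5 requires permanent discontinuation for Grade 3 or 4 infusion-related reactions and spares a Grade 3 reaction that improves by at least one grade within 6 hours. This is close to the structure of the specific row, although improvement by a grade is not the same test as resolution.

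These arguments are good evidence of intent, and they stand. A reader might infer from the clash that the protocol is silent on which rule prevails. That goes too far, because all three indications favour the specific row. None of them settles the wording, however. The sentence is an exclusion and not a criterion, so satisfying one criterion does not clearly defeat it. The narrower scope is nowhere written, and the reason given reaches every grade.

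A reader might also infer that toxicity was undercounted in escalation or that 68 mcg is unsound. The document does not support this. It shows no misclassified event. Section 6.4 required the study team to review all adverse events of Grade 2 or higher before moving to a higher dose level, and Section 6.3.4.1 based the decisions on all available safety data. In Phase 2 the trigger is not the only safeguard, since Section 9.9 has the IDMC monitor safety about every 4 months.

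The size of the single-patient shifts is also no special defect of this rule. Any one DLT moves a cohort of three or six by the same amount.

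**Conclusion.** The inconsistency is real as written but minor. For Grade 4 and unresolved Grade 3 infusion reactions, Table 6-3 gives opposite classifications depending on the row read. Context points to the infusion-related reaction row without saying that it prevails. The definition underlies the Phase 1 primary endpoint and is still in use through the Phase 2 trigger, so it deserves to be put right.

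The Phase 1 shifts of 16.7 or 33.3 points are the most that one reclassified patient could cause, and only if that patient had no other DLT. The Phase 2 counts rest on the assumption that the denominator is the planned cohort size. The dose is already chosen, no disputed event is reported, and crossing the trigger leads only to a teleconference on whether enrollment should continue. The conclusion says nothing against the choice of 68 mcg or the Phase 2 ORR analysis.

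**What to change.** Keep the last sentence of the Other AEs row, but limit it to Grade 1–2 infusion reactions and Grade 3 infusion reactions resolved within 6 hours. The infusion-related reaction row and the header then govern Grade 4 and unresolved Grade 3 reactions, and the two rows agree on every line of the table above. State that the Phase 2 trigger in Section 6.3.4.2 uses this definition.

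Deleting the sentence looks simpler but would change the rule. It would open the discretionary route to Grade 1–2 infusion reactions that delay dosing by more than 7 days in Cycle 1, which the present text blocks on either reading.

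For Phase 1, do not redefine the endpoint after the fact. Report DLT incidence by the rule that was applied during escalation, and state that rule. Check the Phase 1 listing for Grade 4 or unresolved Grade 3 infusion reactions, and disclose any that was not counted.

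The cost is one reworded sentence, one check of a listing and, if an event is found, one disclosure in the report. Dose, sample size and the Phase 2 ORR analysis do not change.

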6.5 Concomitant Therapy

Concomitant therapy will be continuously monitored through the 90-day safety follow up.

6.5.1 Permitted Concomitant Therapy

Concomitant medications and therapies deemed necessary for the supportive care and safety of the patient are allowed in general. Examples include anti-diarrheal medications, anti-emetics, or electrolyte supplementation.

Patients must be told to notify the investigational site staff about any new medications, herbal remedies, or dietary supplements that he or she takes after the start of the study treatment, regardless of treatment duration. All concomitant medications and significant non-drug therapies (including physical therapy, herbal or natural medications, and blood transfusions) administered during the study must be listed on the Concomitant Medications eCRF.

IV hydration required to manage toxicity associated with any of the study medications (e.g., hypotension) and any IV hydration administered prior to study drug dosing should be recorded in the Concomitant Medications eCRF.

6.5.2 Permitted Concomitant Therapy Requiring Caution

Treatment with hematopoietic colony-stimulating growth factors (e.g., G-CSF, GM-CSF, M-CSF or erythroid stimulating agents) may not be initiated during the first cycle in any arm of the study, unless the patient has already experienced a DLT. If a patient is using erythropoiesis-stimulating agent prior to enrollment (beginning at least 2 weeks before start of study treatment), they may continue at the same dose.

Anti-coagulant therapy is permitted if the patients are already at stable doses of warfarin or stable doses of low molecular weight heparin for > 2 weeks at time of first dose. Prophylactic use of low molecular weight heparin during the inpatient hospitalization is allowed. International normalized ratio should be monitored as clinically indicated per investigator's discretion. Ongoing anti-coagulant therapy should be temporarily discontinued to allow tumor biopsy according to the institutional guidelines.

Anti-hypertensives are allowed as concomitant medications; however, because transient hypotension has occurred during infusions of IMCgp100 and monoclonal antibodies, **treatment with anti-hypertensives should be held 24 hours before and 24 hours after IMCgp100** in the first 6 weeks of treatment and thereafter at the discretion of the principal investigator, unless discussed and agreed with the Sponsor's Medical Monitor.

6.5.3 Prohibited Concomitant Therapy

During the course of the study, patients may not receive other additional investigational drugs, agents, devices, chemotherapy, or any other therapies that may be active against cancer. Additionally, no other systemic therapeutic monoclonal antibodies, except for denosumab and tocilizumab if required for patient care, and no immunosuppressive medication may be administered while on this study, unless prescribed to manage toxicity. While systemic corticosteroid therapy will interfere with the mechanism of action of the study medications, its use is recommended in some settings.

The use of systemic corticosteroid therapy is permitted/recommended in the following settings: (1) infusion reactions, (2) immune-mediated toxicities and toxicity management as directed in [Table 6-5](#) (e.g., hypotension not resolving with fluid support), and (3) replacement-dose steroids in the setting of adrenal insufficiency (patients with a pre-existing history of adrenal crisis are excluded from study participation, see [Section 5.3](#) Exclusion Criteria). Any additional uses of systemic corticosteroid therapy during the course of the study should be discussed with the Sponsor Medical Monitor.

